**ACCELEROMETER MOTION TO MEASURE MUSCLE FATIGUE IN CRITICALLY ILL
PATIENTS**

NCT04166630

Date: May 27, 2019

IRB00109793

1. Full title: Accelerometer motion to measure muscle fatigue in critically ill patients

Short title: ICU Acquired Weakness

Principal Investigator: [name], MPH

Co-Investigators: [name]
[name]

Updated Draft Date: May 27, 2019

2. Introduction and background

The primary purpose of this study is to develop a procedure to identify intensive care unit (ICU) acquired weakness. This condition occurs in a subset of people admitted into the ICU, and is associated with a 30% increased risk of death before discharge from the ICU.¹ There are currently major limitations in the ability to diagnose ICU acquired weakness, making it difficult to study.² The goal is to develop a non-invasive test that can be administered to both responsive and non-responsive patients. The current proposal will focus on replicating the results of previous research using motion detecting accelerometers to measure fatigue in human skeletal muscles (Willingham and McCully). This study is designed to test out the procedures in patients who have been transferred from the ICU to a lower level of care so that follow-on studies can be designed to help mitigate this condition in the ICU.

3. Objectives

Objective 1: To identify patterns of muscle fatigue that are distinct for patients with ICU acquired weakness

Objective 2: To identify differences in accelerometer data that appear only in the ICU acquired weakness group for later use as diagnostic criteria.

Objective 3: To develop a diagnostic tool for identifying ICU acquired weakness earlier in the patient's care.

The procedures outlined in this study will advance this objective by providing data that can be analyzed based on whether the subjects have ICU acquired weakness or not based on the current testing procedures.

4. Study Design and Methods

Subjects will undergo a clinical strength assessments to classify them based on whether they test positive for ICU acquired weakness. Manual muscle testing will be performed based on the medical research council (MRC) score. A score of < 48 will classify the subject was having ICU acquired weakness placing them in the "weak" group. Subjects with scores exceeding 48 will be placed into the "not weak" group.

Potential subjects will be approached regarding participation in this study. They will be provided with a written consent form, and allowed adequate time to read the form. After reading, they will

be given a chance to ask questions. If they decide to participate, they will be asked to sign the consent form.

Subjects will then be asked to fill out a health history form. The subjects will then be escorted to a clinical electrical stimulator. We plan to test a variety of skeletal muscles to ensure mastery of the technique. Conductive electrodes will be on the skin at each end of the tested muscle(s). Each subject will have two target muscle groups tested (extensor carpi radialis longus, and tibialis anterior). Each muscle will be stimulated at three separate stimulation frequencies (2 Hz, 4 Hz, and 6Hz) over 3 minutes each, for a total of 9 minutes of stimulation per muscle. The clinical electrical stimulator will then deliver mild electrical stimulations to the muscle (20-100 mA). This intensity of stimulation typically produces only mild discomfort typical of muscle contraction. The clinical stimulator has a maximum output of 110 mA, phase duration 1,000 microseconds, 250 Hz. Any stimulation delivering 25 microcoulombs or higher cannot travel through the thorax because of the risk of cardiac arrhythmias. All stimulations applied in this study will be below this threshold. The stimulation frequencies listed above will be within this safety margin.

The accelerometer used throughout the study will be an Axivity AX3 wireless accelerometer. It will be placed on the muscle belly using double sided tape between the two stimulating electrodes.

Fatigue will be defined as a drop in acceleration from peak acceleration. This will be measured using a triaxial accelerometer over 3 separate stimulation frequencies for a total of 9 minutes of testing per muscle. The device will record 2,160 individual muscle twitches. The highest acceleration over a single muscle twitch will be used as the peak acceleration. The data will then be normalized to this peak acceleration to quantify the percentage of maximal acceleration of each twitch.

The electronic stimulator is currently FDA approved for use in clinical patients so a device determination is not being requested. The accelerometer is passively recording accelerations, with no energy input to the patient. The FDA currently states the following as approved uses for clinical electrical stimulators:

INDICATIONS FOR USE

1. Relaxation of muscle spasms
2. Prevention or retardation of disuse atrophy
3. Increasing local blood circulation
4. Muscle re-education
5. Immediate post-surgical stimulation of calf muscles to prevent venous thrombosis
6. Maintaining or increasing range of motion

Powered muscle stimulators should only be used under medical supervision for adjunctive therapy for the treatment of medical diseases and conditions. Our intended use for the clinical electrical stimulator is to prevent disuse atrophy.

Risks & Discomforts: The risk of pain or discomfort associated with the use of the stimulator is very small and every effort will be made to minimize this. The electrical stimulation procedure occurs at a very low current (20-40 milli-amperes) and is not typically associated with pain. There may be an unfamiliar sensation as the muscle contracts, but the majority of subjects will not find this to be uncomfortable. In the event a subject does not tolerate the stimulation, testing on that

subject will cease. Patients may decide not to continue with higher frequencies at any point during the study.

Another risk of participation in the study is a breach of confidentiality. Please refer to the 'Data and Safety Monitoring' section below for a description of how your personally identifiable health information will be protected. No personal information, including names or email addresses, will be made available to anyone outside of Grady, Emory or the GSU team.

There are no psychosocial risks anticipated from this study. If the patient is uncomfortable or wishes to terminate their participation in the study at any time, they may do so. This will not affect their health care treatment. Formal removal from the study can be done by contacting any of the individuals overseeing the study or members of the individual's normal care team at Grady.

Potential Benefits: The patient may or may not receive a direct benefit from participating in this study. The anticipated benefits involve helping patients better manage their condition and follow treatment plans. The information gained from the study may help improve care for future patients.

Data storage: Strict patient confidentiality will be maintained. Data other than the health history forms will be collected via a triaxial accelerometer and downloaded directly to a Georgia State University computer. This data will be stored on the computer and backed up to a digital storage device that is locked inside filing cabinet inside a locked office. Only the researchers listed on this application will have access to the data. Following the completion of this study, data will be maintained on a university computer. Any paper records will be stored in the manner listed above. All patient information will be de-identified prior to post-study analysis.

5. Participant selection

Requested Sample Size: 150 (extra 50 to account for subject drop outs)

Inclusion criteria:

1. Patients ≥ 18 years of age
2. Patients transferred from the ICU to a lower level of care within the past 7 days
3. Mechanical ventilation for greater than 7 days while in the ICU
4. Ability to understand English and provide written consent

Exclusion criteria:

1. Vulnerable populations including: patients who are pregnant or prisoners
2. Patients who are unable to understand English or provide written consent

Subject recruitment plan:

Screening for eligibility: Targeted patients will include those recently transferred from the ICU to a lower level of care within the hospital. Following routine care, patient records will be reviewed and patients will be asked if they are interested in joining this study and if they meet the aforementioned inclusion and exclusion criteria.

Withdrawal from study: Formal removal from the study can be done by contacting any of the individuals overseeing the study or members of the individual's normal care team at Grady. This

can be done at any time without affecting the patient's ability to obtain routine follow-up care from the post-op clinic or care staff.

Informed consent: Consent will be obtained from patients by a trained research assistant or trained member of the study staff. As mentioned above, patients will be identified as meeting inclusion criteria at the time of transfer from the ICU. If they are eligible, the research assistant will approach them with the opportunity of enrolling in the study. At the time, all potential risks, benefits, and procedures related to participating in the study will be explained as described on the informed consent form. The patients will be given the attached informed consent form and, in the case that they sign it, will begin the on-boarding process for enrollment. All patients have the option to avoid enrollment into the study and can end participation in the study at any time, as described above. Patients will be randomly selected and enrolled by research assistants, rather than directly by the principal investigator, minimizing the risk of coercion.

6. Statistical Analysis

Data will be split into 2 groups (weak vs non-weak) based on clinical strength assessment scores. A 2 factor ANOVA will be used to compare peak acceleration, time to peak acceleration, end acceleration, and fatigue ratio based on group (weak vs non-weak) and stimulation frequency (2 Hz, 4 Hz, 6 Hz). We are collecting 9 minutes of accelerometer data for each muscle, and MRC scores for each subject. A post-hoc analysis with Bonferroni correction will be used to identify where differences occur.

7. Adverse event reporting

The probability of adverse events remains extremely low given the nature of this intervention, but patients can report all events directly to the study staff. Depending on the nature of the event, the individual's participation in the study may be terminated. In the case of a data leak or HIPAA violation, the study staff will jointly address the nature of the leak and determine if any PHI has been leaked. Beyond this, standard HIPAA reporting guidelines will be followed.

8. Data and Safety Monitoring Plan

No personally identifiable (PI) information will be shared with anyone outside of the research team or patient's care team. Any data shared following completion of the study will be de-identified prior to use, protecting the patients' PHI and abiding by the HIPAA Privacy Rules. The only foreseeable disclosure of data beyond the study is in the case of publication of data.

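### Section 2 and Objectives 2 and 3 aim at identifying weak patients, but section 6 plans only group comparisons and no measure of how well any accelerometer measure separates individual patients.

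*Combined protocol and SAP*

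**What the plan says.** Section 2 states: "The primary purpose of this study is to develop a procedure to identify intensive care unit (ICU) acquired weakness". It then narrows the present proposal to repeating earlier accelerometer work on muscle fatigue, and adds: "This study is designed to test out the procedures in patients who have been transferred from the ICU to a lower level of care". Further studies are foreseen.

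In section 3, Objective 1 concerns fatigue patterns that distinguish weak patients. Objective 2 is "To identify differences in accelerometer data that appear only in the ICU acquired weakness group for later use as diagnostic criteria". Objective 3 begins "To develop a diagnostic tool for identifying ICU acquired weakness earlier in" the course of care. The sentence after it reads in part: "The procedures outlined in this study will advance this objective by providing data", to be analysed by weakness status.

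Section 4 defines the reference groups by MRC score: "A score of < 48 will classify the subject was having ICU acquired weakness". Section 5 gives the size: "Requested Sample Size: 150 (extra 50 to account for subject drop outs".

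Section 6 splits patients into weak and non-weak. A two-factor ANOVA (group, and stimulation frequency at 2, 4 and 6 Hz) compares four measures: peak acceleration, the time taken to reach it, acceleration at the end, and the fatigue ratio. Bonferroni-corrected post-hoc tests follow. No section mentions an ROC curve, AUC, sensitivity, specificity, a cut-off on an accelerometer measure or a classification model.

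**The concern.** An ANOVA asks whether group means differ. A diagnostic criterion has to separate individual patients, and two groups can differ clearly in mean while overlapping heavily. Objective 2 defers the use of the criteria, but it gives this study the task of finding them. If that choice rests on the ANOVA result, a measure with little ability to tell weak from not-weak patients could be carried forward. The follow-on studies would then be designed without an estimate of discrimination, although every patient supplies both accelerometer data and an MRC score.

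**Working it through.** **Inputs from the documents.** 150 requested, 50 of them for drop-outs, so 150 − 50 = 100 completers. This agrees with 100/(1 − 1/3) = 150. No alpha, power, effect size, standard deviation or weak share is given, so the 150 cannot be derived further. Candidates: 4 measures × 2 muscles × 3 frequencies = 24.

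**Assumptions, not in the documents.** Two-sided 0.05; 25% to 50% weak (25/75 or 50/50); one value per patient; normal data with equal variance; each group contrast treated as a two-sample t-test with 98 df. The last simplifies the planned ANOVA.

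**What a just-significant contrast means.** d = t × √(1/n₁ + 1/n₀), AUC = Φ(d/√2), and sensitivity = specificity = Φ(d/2) at the midpoint cut-off. Uncorrected, t = 1.984.

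- 50/50: d = 1.984 × 0.200 = 0.397; AUC = Φ(0.281) = 0.61; sensitivity = specificity = 0.58.
- 25/75: d = 1.984 × 0.231 = 0.458; AUC = Φ(0.324) = 0.63; sensitivity = specificity = 0.59.

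The scope of the Bonferroni correction is not specified. Dividing alpha by 3 gives AUCs of 0.635 (50/50) and 0.655 (25/75). Dividing by 24, as a strict bound, gives 0.67 and 0.70.

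**How often a middling marker is significant.** A true AUC of 0.70 means d = √2 × Φ⁻¹(0.70) = 0.742 and sensitivity = specificity of about 0.64, so roughly a third of patients are misclassified. Power from the noncentral t:

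| Alpha | 50/50 | 25/75 |
|---|---|---|
| 0.05 | 96% | 89% |
| 0.05/3 | 90% | 78% |
| 0.05/24 | 71% | 52% |

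A marker with AUC 0.80 (d = 1.190) is significant in over 99% at alpha 0.05 or 0.05/3.

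**What an AUC with an interval would add.** Hanley–McNeil: SE² = [A(1 − A) + (n₁ − 1)(Q₁ − A²) + (n₀ − 1)(Q₂ − A²)]/(n₁n₀), with Q₁ = A/(2 − A) and Q₂ = 2A²/(1 + A). The 95% half-width is 1.96 × SE.

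| Observed AUC | 50/50 | 25/75 |
|---|---|---|
| Just significant, uncorrected (0.61; 0.63) | 0.50 to 0.72 | 0.50 to 0.76 |
| 0.70 | ± 0.102: 0.60 to 0.80 | ± 0.126: 0.57 to 0.83 |
| 0.80 | ± 0.087: 0.71 to 0.89 | ± 0.111: 0.69 to 0.91 |

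The first row excludes 0.80. The second row reaches it.

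**Multiplicity.** With 24 uninformative measures, 24 × 0.05 = 1.2 unadjusted intervals would be expected to exclude 0.5. Bonferroni-adjusted intervals use z = Φ⁻¹(1 − 0.05/48) = 3.078, so they are 3.078/1.96 = 1.57 times as wide. The just-significant intervals become about 0.44 to 0.78 (50/50) and 0.42 to 0.83 (25/75).

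**Chosen cut-offs.** In 20,000 simulated studies at AUC 0.80, a cut-off picked by the Youden index on the same data overstates sensitivity + specificity − 1. It shows 0.509 against a true 0.428 (50/50), and 0.521 against 0.425 (25/75), an excess of 0.08 to 0.10.

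**The case against.** The best defence is scope. Section 2 confines this proposal to replication and to trying out procedures. Objective 2 speaks of later use, and the sentence after Objective 3 most naturally defers the tool itself. A group comparison fits such a step. This stands in large part. A reader might infer that the ANOVA is the wrong analysis, or that the study fails because it will not produce a validated test. The documents support neither: the ANOVA answers Objective 1, partly serves a group-level reading of Objective 2, and no validated tool is promised from this study alone.

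Second, section 6 does not restrict reporting to p-values, and under the model used above the AUC follows from group means and standard deviations. That is true under equal-variance normality. But section 6 commits to no such summaries, and the patient-level data give the AUC without that assumption.

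Third, a reader might infer that adding AUCs would sort good markers from middling ones. It would not: an observed 0.70 has an interval that reaches 0.80 under either split. Unadjusted intervals for 24 measures would also invite chance findings. Both points stand and limit the fix.

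Fourth, the sponsor could simply reword Objectives 2 and 3 as exploratory and leave accuracy to a later study. That would remove the mismatch, but would leave information already collected unused.

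**Conclusion.** The point holds as a gap between aims and analysis that is cheap to close. The diagnostic aims have no matching measure of discrimination, and significance cannot stand in for one: with about 100 completers, a just-significant contrast corresponds to an AUC of about 0.61 to 0.63 uncorrected. A strict correction raises this to about 0.67 to 0.70 and so narrows the gap without closing it.

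The sizes are illustrations resting on the assumed alpha, weak share, normality and t-test simplification. They show no figure in the documents to be wrong. The added AUCs would help mainly to flag clearly poor markers, around 0.61 to 0.63. Even that is weaker with fully adjusted intervals when only a quarter of patients are weak.

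Section 4 places scores below 48 in one group and says "Subjects with scores exceeding 48 will be placed into the" other, so a score of exactly 48 falls in neither. That is a separate issue, affects the ANOVA equally, and adds no weight here.

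**What to change.** Keep the ANOVA and its Bonferroni correction. Add to section 6, for Objectives 2 and 3:

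- The AUC with 95% confidence interval of each of the four measures, by muscle and frequency (24 in all), against the MRC-defined groups. All are reported and labelled exploratory.
- Either simultaneous intervals (for example Bonferroni-adjusted) or an explicit caution about multiplicity.
- A statement that a measure is called a candidate diagnostic criterion on its AUC and interval alongside the corrected test, not on the p-value alone.
- An optimism correction, by bootstrap or cross-validation, for any cut-off chosen from the data.

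Reword Objective 3 as providing data towards a diagnostic tool.

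The cost is one paragraph in section 6, one reworded objective and a little more analysis, with no new patients or measurements. The downside is modest precision: the AUCs cannot reliably separate a marker of 0.70 from one of 0.80 or validate a good one. They would also come from consenting patients who have already left the ICU, so they do not by themselves support earlier use or use in non-responsive patients.

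### Candidate diagnostic criteria are chosen and sized in the same patients, so their reported strength may be overstated, and Bonferroni does not correct this

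*Combined protocol and SAP*

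**What the plan says.** Section 3 sets two objectives that look beyond a group comparison. Objective 2 is "To identify differences in accelerometer data that appear only in the ICU acquired weakness group for later use as diagnostic criteria", and Objective 3 is "To develop a diagnostic tool for identifying ICU acquired weakness earlier in the patient's care".

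Section 6 gives the only analysis. "Data will be split into 2 groups (weak vs non-weak) based on clinical strength assessment scores". Then "A 2 factor ANOVA will be used to compare peak acceleration, time to peak acceleration, end acceleration, and fatigue ratio based on group" and stimulation frequency (2, 4 and 6 Hz). Finally, "A post-hoc analysis with Bonferroni correction will be used to identify where differences occur". Section 4 adds the muscles: "Each subject will have two target muscle groups tested (extensor carpi radialis longus, and tibialis anterior".

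Section 5 gives the numbers: "Requested Sample Size: 150 (extra 50 to account for subject drop outs". Section 2 says that the procedures are being tried out "so that follow-on studies can be designed to help mitigate this condition in the ICU".

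No section describes a hold-out sample, cross-validation, resampling, shrinkage or a validation cohort. Alpha, sidedness, the Bonferroni family, the expected share of weak patients, and any effect size or SD are also unstated.

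**The concern.** Section 6 tests many contrasts to find where the groups differ, and Objective 2 takes what is found forward as candidate criteria. A contrast kept because its estimate cleared a threshold has, on average, an estimate that is too large. The less power there is, the larger the excess. Multiplicity correction addresses a different problem: it lowers the chance that a null contrast is kept. A stricter threshold in fact raises the average overstatement among the contrasts that survive it.

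At stake is how strong the proposed markers appear. A reader of the results would take the reported weak versus non-weak difference as the separation to expect in new patients, and nothing in the plan warns that it may be smaller.

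**Working it through.** **Inputs from the documents**
- Evaluable patients: 150 requested, 50 of them for drop-out, so 150 − 50 = 100 (section 5). With no effect size, SD, alpha or power stated, 150 cannot be reproduced as a powered sample size.
- Contrasts: 4 measures × 3 frequencies (section 6) × 2 muscles (section 4) = 24 at most.

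**Assumptions**
- Two-sided 0.05, Bonferroni family m between 3 (the frequencies) and 24 (all contrasts).
- Split 50:50, with 25:75 as an uneven alternative.
- True standardised difference d from 0.2 to 1.0.
- Simple two-group contrasts. How section 6 handles repeated frequencies and muscles within a patient could change the standard errors, but not the direction of the bias.

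**Step 1: smallest difference that can pass**

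SE = √(1/n₁ + 1/n₂) = √(1/50 + 1/50) = 0.20. The critical z is 2.394 for m = 3 and 3.078 for m = 24. The smallest passing difference is therefore 2.394 × 0.20 = 0.48, or 3.078 × 0.20 = 0.62. A true d of 0.3 can pass only if it is overestimated.

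**Step 2: expected overstatement of a contrast that passes**

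With λ = d/SE and critical value c, and ignoring the negligible opposite tail, ratio = [λ + φ(c − λ)/Φ(λ − c)]/λ.

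- d = 0.3, m = 3: λ = 1.5; (1.5 + 0.2675/0.1857)/1.5 = 2.94/1.5 = 1.96. The chance of passing is 19%.
- d = 0.3, m = 24: (1.5 + 0.1149/0.0573)/1.5 = 3.51/1.5 = 2.34. The chance of passing is 6%.
- d = 0.8, m = 3: λ = 4; (4 + 0.1099/0.9459)/4 = 1.03. The chance of passing is 95%.

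| True d | Ratio at 50:50, m = 3 to 24 | Ratio at 25:75, m = 3 to 24 |
|---|---|---|
| 0.2 | 2.85 to 3.44 | 3.26 to 3.96 |
| 0.3 | 1.96 to 2.34 | 2.23 to 2.68 |
| 0.4 | 1.53 to 1.79 | 1.73 to 2.04 |
| 0.5 | 1.29 to 1.48 | 1.44 to 1.67 |
| 0.8 | 1.03 to 1.08 | 1.08 to 1.16 |
| 1.0 | 1.00 to 1.01 | 1.01 to 1.05 |

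If all 150 patients are evaluable at 75:75, d = 0.3 gives 1.64 to 1.94.

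**Step 3: keeping only the strongest contrast**

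Simulating 24 contrasts with equal true effects at 50:50, and correlation from 0 to 0.8, the largest passing contrast is overstated 1.45 to 1.78 times at d = 0.5 and 1.22 to 1.49 times at d = 0.8. With unequal effects (mean 0.4, SD 0.2, correlation 0.5), the strongest contrast reads about 0.88 to 0.89 against its own true value of 0.71 to 0.72, roughly 25% too high.

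**Step 4: what a bootstrap correction recovers**

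Simulated with 100 patients, 50:50 or 30:70, correlation 0.3 or 0.6, and alpha 0.05/3:
- True d = 0.3, strongest contrast: apparent 0.64 to 0.70, corrected 0.43 to 0.49.
- Effects that vary, strongest contrast: apparent 0.86 to 0.94, corrected 0.73 to 0.77, against a true 0.69 to 0.73.

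The correction moves towards the truth in both cases, but is clearly incomplete in the first.

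**The case against.** Four points can be made against this.

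- **The selection rule is inferred.** Neither Objective 2 nor section 6 says that a significant contrast becomes a criterion. Muscle is not an ANOVA factor, and the post-hoc tests might compare frequencies, or only the group main effect (4 measures × 2 muscles = 8 tests). This stands as a limit on the count: 24 is a maximum. It does not remove the concern, because section 6 offers no other route to Objective 2, and the bias arises with any number of tests.
- **A useful marker would have a large effect, where the bias is slight.** With AUC = Φ(d/√2), d = 0.8 is an AUC of only about 0.71. This is fair for contrasts that merely pass. It is weaker if the strongest is singled out (step 3), and the plan gives no reason to expect large effects.
- **The bootstrap does not fully cure the problem.** Correct: resamples centre on an estimate that is already inflated. At a true d of 0.3, passing contrasts fall only from 0.58–0.64 to 0.48–0.52. The correction still helps, but its limits must be stated.
- **Follow-on work may put this right.** It may, but section 2 mentions those studies for mitigation and says nothing of validating criteria.

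A reader might go further and infer that follow-on studies will be sized on these estimates and so be too small. No section says that any effect size will be carried forward for that purpose. A reader might also infer that the wrong frequency or muscle will be chosen. Calculations that give every contrast the same true effect cannot show that, and the documents do not speak to it.

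**Conclusion.** The point holds as a risk of overstatement that the plan neither corrects nor acknowledges. The direction is certain on average for any contrast kept because it passed. The size is not derivable from the documents. Under the even-split assumption with 100 evaluable patients, it runs from negligible at a true d of 0.8 or more, through about 1.3 to 1.5 times at 0.5, to about twofold at 0.3, and about threefold at 0.2. A 25:75 split takes the top of the range to about four times.

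Twofold is therefore one point on a range, not a ceiling or a forecast. If a selected contrast is truly null, its whole estimate is error and no ratio applies. This should be corrected in the analysis plan, but it does not undermine the data collection or the group comparison itself.

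**What to change.** Add a paragraph to section 6:

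1. State the selection rule: alpha, sidedness, the Bonferroni family, which contrasts are tested, and whether all that pass or only the strongest go forward under Objective 2. Without this, the selection cannot be repeated.
2. For any contrast put forward, repeat the whole selection step in bootstrap resamples of patients, keeping all of a patient's muscles and frequencies together.
3. Report the optimism-corrected difference with an interval, and how often the contrast is selected, beside the apparent difference.
4. State that the correction is only partial when true effects are small, and that the criteria are exploratory until tested in new patients.

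The plan should not present the corrected value as safe for sizing later studies, because at small true effects it is still too high.

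The cost is a short paragraph and modest computing, with no new patients, visits or measurements. The downside is a less favourable reported effect for whichever marker is chosen.

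### Section 4 plans stimulation at up to 100 mA, but its Risks & Discomforts paragraph describes the same procedure as 20-40 mA

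*Combined protocol and SAP*

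**What the plan says.** All of the relevant text is in section 4 of the combined protocol and SAP.

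- **Current, in the description of the procedure:** "The clinical electrical stimulator will then deliver mild electrical stimulations to the muscle (20-100 mA". The next sentence says that this intensity usually causes no more than mild discomfort.
- **Current, under Risks & Discomforts:** "The electrical stimulation procedure occurs at a very low current (20-40 milli-amperes) and is not typically associated with pain". The paragraph adds that most subjects will not find the sensation uncomfortable.
- **Device capability:** "The clinical stimulator has a maximum output of 110 mA, phase duration 1,000 microseconds, 250 Hz".
- **Charge threshold:** "Any stimulation delivering 25 microcoulombs or higher cannot travel through the thorax because of the risk of cardiac arrhythmias".
- **Commitment on charge:** "All stimulations applied in this study will be below this threshold".
- **Support offered for it:** "The stimulation frequencies listed above will be within this safety margin". The frequencies are 2, 4 and 6 Hz.
- **Site of stimulation:** "Each subject will have two target muscle groups tested (extensor carpi radialis longus, and tibialis anterior", with electrodes on the skin at the two ends of the muscle. The same paragraph also says "We plan to test a variety of skeletal muscles to ensure mastery of the technique".

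**The concern.** Current is the setting that fixes how strongly these patients are stimulated, and the protocol gives it two upper limits. Someone judging the risk from the risk paragraph would assess 40 mA. Someone operating the stimulator from the procedure text may go to 100 mA. The reassurance about pain is attached to the lower range only. Either the risk paragraph understates the planned maximum, or the procedure allows more current than intended.

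The charge commitment raises a smaller, linked question. The plan undertakes to keep every stimulation below 25 microcoulombs and then points to the stimulation frequencies. Charge per phase depends on current and phase duration. It is the same at 2, 4 and 6 Hz, so frequency cannot show that the limit is met. The setting that could show it, the operating phase duration, is not stated. How long the phase may be depends on which current ceiling is right.

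**Working it through.** **1. The two current ranges**

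Inputs, both from section 4: 20-100 mA (procedure) and 20-40 mA (Risks & Discomforts).

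- Lower ends: 20 and 20 mA, which agree.
- Upper ends: 100 and 40 mA. Difference 100 - 40 = 60 mA; ratio 100/40 = 2.5.

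Three readings could reconcile them, and the text supports none:

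- Different muscles or frequencies: neither sentence names one.
- A typical range against a permitted range: in the risk sentence the qualifier applies to pain, not to the current.
- Superseded text or a damaged table: both are complete sentences of current running text.

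**2. The charge commitment**

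The plan's own figure is a limit: below 25 microcoulombs for every stimulation. It can be neither reproduced nor refuted, because no operating phase duration is given. The 1,000 microseconds is listed with 110 mA and 250 Hz as what the stimulator can deliver. The study runs at 2-6 Hz, so that line describes the device and not the study setting.

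Formula, assuming a rectangular phase: charge (microcoulombs) = current (mA) x phase duration (microseconds) / 1,000. Frequency does not enter.

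Duration at which 25 microcoulombs is reached:

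- at 100 mA: 25 x 1,000 / 100 = 250 microseconds
- at 40 mA: 25 x 1,000 / 40 = 625 microseconds

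Charge over an assumed range of durations from 100 microseconds to the device figure of 1,000:

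| Assumed phase duration (microseconds) | Charge at 20 mA | Charge at 40 mA | Charge at 100 mA |
|---|---|---|---|
| 100 | 2 | 4 | 10 |
| 200 | 4 | 8 | 20 |
| 250 | 5 | 10 | 25 |
| 400 | 8 | 16 | 40 |
| 625 | 12.5 | 25 | 62.5 |
| 1,000 | 20 | 40 | 100 |

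The limit is strict, so a value of 25 does not meet it. Below 250 microseconds both ceilings comply. From 250 to just under 625, the 40 mA ceiling complies and the 100 mA ceiling does not. From 625 upward neither ceiling complies. At 1,000 microseconds the current would have to stay under 25 x 1,000 / 1,000 = 25 mA. The rows are chosen for illustration, and how many of them pass or fail has no meaning.

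**The case against.** The best answer to the current mismatch is that the protocol does not hide the higher range. It describes mild discomfort directly after stating 20-100 mA. It also stops testing in a subject who does not tolerate the stimulation, lets patients decline the higher frequencies, and lets them leave at any time. All of this stands. It limits the harm and rules out the inference that discomfort above 40 mA goes undescribed. It does not say which ceiling applies.

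On charge, the defence is stronger. The commitment binds whatever phase duration is chosen: a longer phase simply forces a lower current. The threshold is worded for stimulation through the thorax, while the named muscles are in the forearm and lower leg. The wish to test a variety of muscles is loosely put, but no thoracic muscle is named. The sentence on frequencies may mean only that 2-6 Hz lies well within the device's 250 Hz, although it does not say so. What remains is unclear support for a limit and an unstated setting.

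A reader might infer two stronger things. One is that the study would exceed 25 microcoulombs. The documents do not show this, since a phase under 250 microseconds complies even at 100 mA. The other is that patients are told the lower current. Section 5 (Informed consent) says that risks are explained as described on the consent form. That form was not available, so what patients are told is unknown.

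**Conclusion.** The current range is wrong as written in one of two places. The ceilings are 100 and 40 mA, a factor of 2.5, for one procedure in one section, and nothing reconciles them. This rests on the protocol text alone and needs no assumption. The documents do not show which figure is the intended one. The point should be fixed because a risk description ought to match the planned stimulation. No harm to patients has been demonstrated.

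The charge point is minor. Frequency cannot support a limit on charge per phase, and the operating phase duration is missing. The durations of 250 and 625 microseconds assume a rectangular phase. This is a gap in the wording of a safety commitment, not a breach of it.

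**What to change.** 1. Give one current range throughout section 4. If up to 100 mA will be used, change Risks & Discomforts to 20-100 mA and carry over the mild-discomfort wording from the procedure text. If not, cap the procedure at 40 mA. The choice belongs to the investigators.
2. Check the consent form against the chosen range.
3. Replace the sentence on frequencies with the operating setting that meets the existing commitment: phase duration under 250 microseconds for currents up to 100 mA, or under 625 microseconds for currents up to 40 mA.

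The cost is a wording amendment and a check of the consent form. Sample size, visits and test duration do not change.
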